6. DETERMINATION OF PROTOCOL DEVIATIONS

6.1 Definition of Protocol Deviations

The CSR-reportable PD are defined in accordance with International Conference on Harmonization (ICH) E3 as important PDs related to study inclusion or exclusion criteria, conduct of the trial, subject management or subject assessment resulting in the potential to jeopardize the safety or rights of the trial subjects or the scientific value of the trial. Protocol deviations will be classified as CSR-reportable and non-CSR-reportable.

The Protocol Deviation Specification Document for this study lists all the pre-specified observable and programmable PDs, including their classification, categories, sub categories and impact on the analysis.

CSR-reportable PDs may lead to exclusion of the subject or part of the subject's data from at least the PP analysis set.

The number of subjects in any and by PD category will be summarized by study treatment and overall. Individual subject listings will be provided sorted by subject and by PD category.

6.2 Determination of Protocol Deviations

The source/method of identification can be either observable or programmable. Programmable PDs are those which can be programmed from the data recorded in the clinical database.

Observable PDs are identified by Clinical Research Associates (CRAs) during monitoring or other team members.

A set of listings will be programmed following the Protocol Deviation Specification List to determine and categorize the PDs. These listings will be provided for review on an ongoing basis during the study.

This review will also include PDs captured reported in monitoring reports. The PD review output will include:

- An assessment of CSR-reportable PDs based on blinded clinical data review.
- An assessment of subjects without PDs (e.g., premature withdrawals due to AE, withdrawal of consent) who should be excluded from an analysis set.

Prior to unblinding, all reportable PDs will be evaluated, and the PDs that led to exclusions from analysis sets will be documented and signed off by at least the Biostatistician and the Clinical Scientist.

Statistical Analysis Plan, Protocol Number V87_30

06 MAY 2022 Final Version 1.0

6.3 Exclusions of Individual Values for Safety Analysis

Some local and systemic AEs will be directly measured by the subject and will not be subject to a reconciliation process, even if they are biologically implausible.

Therefore, these implausible measurements will be removed from the analysis but included in listings. Implausible measurements are summarized in the table below:

Table 2 Implausible Solicited Adverse Events

| Parameter | Implausible measurements |
|------------------|---|
| Body temperature | $\leq 33^{\circ}\text{C}$ or $\geq 42^{\circ}\text{C}$ |
| Erythema | For subjects ≥ 6 years: ≥ 900 mm and for subjects < 6 years: ≥ 450 mm Measurements < 0 mm |
| Induration | For subjects ≥ 6 years: ≥ 500 mm and for subjects < 6 years: ≥ 250 mm Measurements < 0 mm |
| Ecchymosis | For subjects ≥ 6 years: ≥ 500 mm and for subjects < 6 years: ≥ 250 mm Measurements < 0 mm |

7. ANALYSIS SET

7.1 All Enrolled Set

Statistical Analysis Plan, Protocol Number V87_30

06 MAY 2022 Final Version 1.0

All screened subjects who provide informed consent and provide demographic and/or other baseline screening measurements, regardless of the subject's randomization and vaccination status in the trial and receive a subject identification (ID).

Demography and baseline characteristics tables as well as subject listings will be produced on the All Enrolled Set.

7.2 All Exposed Set

All subjects in the All Enrolled Set who received at least one dose of study vaccination.

7.3 Full Analysis Set (FAS), Immunogenicity

All subjects in the All Enrolled Set who are randomized, received at least one dose of study vaccination and provided immunogenicity data at any data points.

In case of randomization error, subjects in the FAS sets will be analyzed “as-randomized” (i.e., according to the vaccine the subject is assigned to per randomization).

7.4 Per Protocol Set (PPS), Immunogenicity

All subjects in the FAS Immunogenicity who:

- Correctly receive the vaccine (i.e., receive the vaccine to which the subject is randomized and at the scheduled time points)
- Have no CSR-reportable PD leading to exclusion as defined prior to unblinding.
- Are not excluded due to other reasons defined prior to unblinding or analysis (see section 6.2)
- Have immunogenicity results on Day 1 (before first vaccination) and Day 22 or at Day

Statistical Analysis Plan, Protocol Number V87_30

06 MAY 2022 Final Version 1.0

43 within the defined window around the planned visits.

If a subject is unblinded during the study (except for SUSAR), he/she will be excluded from the PPS.

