4.4 Criteria for Repeat Vaccination in the Study

Prior to receipt of the second study vaccination, subjects must be evaluated to confirm that they are eligible for subsequent vaccination. If subjects meet any of the criteria listed below, they should not receive additional vaccinations.

- Has experienced any immediate allergic reaction after the previous study vaccination
- Has experienced any serious adverse event judged to be possibly or probably related to study vaccination, including hypersensitivity reactions.
- Has developed any clinically significant medical condition which, in the opinion of the investigator, may pose additional risk to the subject if he/she continues to participate in the study.

Subjects who meet any of these criteria must not receive further study vaccinations. However, the subject's parent(s)/LAR(s) should be encouraged to continue study participation of the subject.

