3. STUDY DESIGN

This randomized, observer blind, multi-center clinical trial evaluates the immunogenicity in healthy children ages 6 months to <9 years of 6 vaccine regimens utilizing 6 different formulations including either 1.875, 3.75, or 7.5 μ g HA of pandemic H5N1 influenza strain combined with either 0.125 mL or 0.25 mL MF59, in two intramuscular (IM) injections administered three weeks apart.

Statistical Analysis Plan, Protocol Number V87_30

06 MAY 2022 Final Version 1.0

A total number of 420 subjects will be enrolled to assure at least 150 evaluable subjects for each of the age cohorts as required by the pediatric investigational plan. Subjects <9 years will be randomized to receive either one of the six formulations in 1:1:1:1:1:1 allocation ratio, stratifying according to age cohort (6 months to < 36 months and 3 years to < 9 years of age). The distribution of all enrolled subjects across the two age cohorts should be about 50% in each.

Subjects in each study vaccine group will be scheduled to receive 2 injections of aH5N1 vaccine 3 weeks (21 Days) apart. Each subject will have two periods of study participation: Treatment Period (Day 1 to Day 43 – i.e. 21 days after second injection) and Follow-up Period (Day 44 to Day 387 – i.e. 12 months after second injection).

Blood samples for serology assessments will be collected from each subject on Day 1 (before randomization), Day 22 (before vaccination), Day 43, and Day 202.

Subject Diary Cards will be provided to subjects for recording of local and systemic reactions (solicited adverse events) for 7 consecutive days after each vaccination. All unsolicited adverse events (AEs) will be collected during the treatment period.

In the follow-up period (Day 44 through Day 387), only the following subset of unsolicited AEs and the associated concomitant medications/vaccinations will be collected and documented in the subject's eCRFs: all serious AEs (SAEs), New Onset of Chronic Disease (NOCD), AEs leading to study withdrawal, and Adverse Events of Special Interest (AESIs) (as described in section 7.1 of the current protocol). These data will be captured by interviewing the subject's parent(s) or legally authorized representative (LAR) and/or by reviewing the available medical records.

For further details please refer to section 3.0 of the protocol.

Table 1 Time and Events Table

| | | Treatment period | | | | | Follow-up period | | | |

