7.5 Safety Set

Solicited Safety Set

All subjects in the Exposed Set with any solicited AE data collected, including temperature measurements or use of analgesics/antipyretics.

Unsolicited Safety Set

All subjects in the Exposed Set with results of the unsolicited AE assessments recorded. A record of safety assessment performed at a specific time point, with confirmation of no AE, is considered as AE data hence subject is to be included.

Safety Set

All subjects who are in the Solicited Safety Set or in the Unsolicited Safety Set.

Subjects will be analyzed as “treated” (i.e., according to the vaccine a subject actual received as first dose, rather than the vaccine to which the subject may have been randomized).

All immunogenicity analyses (primary, secondary, and exploratory) will be performed on the PPS Immunogenicity. The primary immunogenicity analyses will be also performed based on the FAS Immunogenicity if the percentage of subjects excluded from the PPS immunogenicity is greater than 5%. All solicited safety analyses will be performed in solicited safety set. All unsolicited safety analyses will be performed on the unsolicited safety set.

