11.2 Primary Objectives Analysis

The primary endpoints in terms of measures of immunogenicity, as determined by the HI and MN assay against the H5N1 pandemic influenza homologous strain include the following:

- Geometric Mean Titer (GMT) on Day 1, Day 22 (3 weeks after the first vaccination) and Day 43 (3 weeks after the second vaccination).
- Geometric mean ratios calculated as follows: Day 22/day 1 or Day 43/Day 1 as determined by HI and MN assays against the homologous H5N1 pandemic influenza strain.
- Percentage of subjects with seroconversion on Day 22 and Day 43.
- Percentages of subjects with HI or MN titers $\geq 1:40$ at Day1, Day 22 and Day 43.

In addition, reverse cumulative distribution plots will be generated to display the distribution of the antibody responses by visit (Day1, Day 22, Day 43 and Day 202) for each of the vaccine groups. The x-axis represents the immunogenicity values, and the scale of the axis is original scale. The y-axis represents the percentage of subjects having at least that immunogenicity value. Due to the discrete values of antibody response, the plot will show a step-wise function. The figures begin at 100%, and then descends to the lowest point on the curve, which is the percentage of subjects having an immunogenicity value equal to the highest observed value.

No hypothesis testing will be applied.

The primary immunogenicity objective analyses will be performed on the PPS Immunogenicity, and will be also performed based on the FAS Immunogenicity if the percentage of subjects excluded from the PPS immunogenicity is greater than 5%.

Statistical Analysis Plan, Protocol Number V87_30

06 MAY 2022 Final Version 1.0

Geometric Mean Titer

Summary statistics (geometric mean, minimum, median, maximum) of the titers will be presented by assessment (Day 1, Day 22, Day 43 or Day 202) and vaccine group for the overall group and separate by each age subgroup.

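### The single per-protocol set in SAP 7.4 lets events at or after the Day 22 bleed remove children from the Day 22 primary results

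*SAP*

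**What the plan says.** **Dosing criterion.** SAP 7.4 gives one immunogenicity PPS. Its first criterion is that children "receive the vaccine to which the subject is randomized and at the scheduled time points". SAP 3 states: "Subjects in each study vaccine group will be scheduled to receive 2 injections of aH5N1 vaccine 3 weeks (21 Days) apart".

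**Sampling criterion.** SAP 7.4 also requires that children "Have immunogenicity results on Day 1 (before first vaccination) and Day 22 or at Day" 43, within the visit window. This concerns samples, not doses. Protocol 8.3.5 has the same dosing criterion and adds that missing titres at some visits do not exclude.

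**Unblinding.** SAP 7.4 excludes any child unblinded during the study, except for a SUSAR, with no link to a visit.

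**Timing and endpoints.** SAP 3 lists the post-baseline samples as "Day 22 (before vaccination), Day 43, and Day 202". The primary endpoints in SAP 11.2 include "Percentage of subjects with seroconversion on Day 22 and Day 43", with GMT, GMR and the proportion with a titre of at least 1:40 at Day 22.

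**Use of the set.** SAP 7.5 states: "All immunogenicity analyses (primary, secondary, and exploratory) will be performed on the PPS Immunogenicity". SAP 7.6 lists no other set. The primary immunogenicity analyses are repeated "based on the FAS Immunogenicity if the percentage of subjects excluded from the PPS immunogenicity is greater than 5" percent.

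**Reasons for no second dose.** Protocol 4.4 bars a second vaccination if, for example, the child "Has experienced any immediate allergic reaction after the previous study vaccination".

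**The concern.** Day 22 is the only look at the response to one dose. The background sections of both documents name a smaller number of vaccinations and a lower antigen dose as aims, and the Day 22 endpoints speak to the first of these.

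A set used for a one-dose result should depend only on what happened up to that bleed. The single PPS goes further, because whether dose 2 was given, and from which kit, is settled after the Day 22 sample is taken. Where dose 2 is withheld for a reaction to dose 1, the reason for exclusion may also be related to antigen or MF59 content, which are the factors under comparison.

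SAP 8.2 argues that missing titres can be treated as uninformative. That argument is about titres that are absent. It does not cover Day 22 titres that exist and are set aside because of later events.

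**Working it through.** **1. The plan's own figures reproduce.** The inputs from SAP 5 are 420 children, up to 14% excluded, and an SD of 0.7 for log10 HI titre. There are six groups and two age cohorts.

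- Evaluable: 420 × (1 − 0.14) = 361.2, which is 180.6 per cohort, 60.2 per group, and 30.1 per group and cohort. SAP 5 gives about 180, 60 and 30.
- 95% CI factor: 10^(±1.96 × 0.7/√n). For n = 30 this is 0.56 to 1.78, and for n = 60 it is 0.67 to 1.50, as SAP 5 states.

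**2. Which children are affected.** Each case assumes a correct dose 1 and an in-window Day 22 titre.

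- *Dose 2 withheld under Protocol 4.4.* This is not a deviation, but the child has not had the vaccine at both scheduled time points and so fails the first criterion.
- *Wrong kit at dose 2.* The child fails the same criterion by not receiving the randomized vaccine.
- *Unblinded after Day 22.* SAP 7.4 excludes.
- *Partial or expired dose 2.* Not settled. SAP 4.1.1 makes this a CSR-reportable deviation. SAP 6.1 allows such a deviation to remove only part of a child's data and leaves the impact to a separate specification document.

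**3. Upper limit on the children recovered.** The documents do not split the 14% by cause. Let s be the share that arises at or after the Day 22 bleed (assumption, full range shown). Then Day 22 n = 420 × [1 − 0.14 × (1 − s)].

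| s | Day 22 n | Per group | CI factor | Per group and cohort | CI factor |
|---|---|---|---|---|---|
| 0% | 361 | 60.2 | 0.67–1.50 | 30.1 | 0.56–1.78 |
| 25% | 376 | 62.7 | 0.67–1.49 | 31.3 | 0.57–1.76 |
| 50% | 391 | 65.1 | 0.68–1.48 | 32.5 | 0.57–1.74 |
| 75% | 405 | 67.5 | 0.68–1.47 | 33.8 | 0.58–1.72 |
| 100% | 420 | 70.0 | 0.69–1.46 | 35.0 | 0.59–1.71 |

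**4. Possible shift in the Day 22 GMT.** Suppose a fraction f of a group is excluded and those children have a Day 22 GMT r times that of the children kept. The log10 mean of all children then exceeds that of the kept children by f × log10(r), so PPS GMT / all-children GMT = r^(−f). Both inputs are assumptions.

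| f | r = 0.5 | r = 2 |
|---|---|---|
| 5% | 1.035 | 0.966 |
| 7% | 1.050 | 0.953 |
| 14% | 1.102 | 0.908 |

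If two groups shift equally, the shift cancels in their GMT ratio. A group that lost more than 14% this way could shift further.

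**5. When the FAS repeat runs.** The trigger is more than 0.05 × 420 = 21 children excluded. With a binomial count out of 420, the probability of 22 or more is above 0.999 at a true exclusion rate of 14%, about 0.94 at 7%, and about 0.44 at 5%.

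**The case against.** The strongest reply is the FAS repeat. The FAS (SAP 7.3) needs only one dose and immunogenicity data at any time point, so it keeps every child described above who has a Day 22 titre. At the planned 14% exclusion the repeat is almost certain to run. A reader might infer that these Day 22 titres are never analysed, and the documents do not support that for the primary endpoints. What remains is that the repeat is conditional and covers primary analyses only. The exploratory factorial ANCOVA of Day 22 titres (SAP 11.4) has no FAS counterpart. The FAS also keeps children given the wrong kit at dose 1 as randomized, so it is not a clean one-dose per-protocol estimate.

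Second, SAP 7.4 does not literally say that both doses are required. That reading follows from the plural in the dosing criterion and the two-dose schedule. The sampling criterion and the note in Protocol 8.3.5 suggest that children with Day 22 data alone were meant to stay. This counts in favour of clarifying the text, because nothing limits the dosing criterion to dose 1 for Day 22.

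Third, fewer children may be affected than first appears. Protocol 4.2 says that children who meet an exclusion criterion before dose 2 need no further blood samples, so some will have no Day 22 titre. A late visit 2 also makes the Day 22 sample late. Visit-specific sets recover neither group. This stands.

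Fourth, the analysis is descriptive, with no hypotheses and no success criteria, and one set keeps largely the same children at Day 22 and Day 43. This stands too, and it limits the consequence.

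**Conclusion.** The point holds as a narrow one. As written, the PPS can remove a valid one-dose result because of something that happened at or after the Day 22 bleed. The clear cases are a withheld dose 2, a wrong kit at dose 2, and later unblinding.

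The size is unknown and probably small. At most about 10 children per group return (60 to 70), and only if every planned exclusion is of this kind. With 5% to 14% of a group excluded and a GMT in those children between half and twice that of the rest, the PPS Day 22 GMT lies between 0.91 and 1.10 times the all-children value. That is well inside the plan's own 95% CI factor of 0.67 to 1.50 at n = 60.

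A reader might go further and infer that the Day 22 comparison is biased towards children who tolerated dose 1. The documents do not support that. They give no link between tolerance of dose 1 and titre, and no count of affected children by group, so neither a bias nor its direction is shown. The case for change is that the rule conditions a primary result on later events without need, and that correcting it is cheap.

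**What to change.** In SAP 7.4, replace the single PPS with one flag per visit. Each flag should depend only on doses, deviations and unblinding up to that visit's sample and keep the Day 1 result already required.

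- **Day 22:** correct dose 1 and an in-window Day 22 result.
- **Day 43:** both doses correct and an in-window Day 43 result.
- **Day 202:** both doses correct and an in-window Day 202 result.

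Use each flag only for its own visit, including in the SAP 11.4 factorial model. State in the deviation specification document which visits each deviation affects. In the same edit, reconcile SAP 4.2, under which unblinded children may be excluded from the PPS, with SAP 7.4, under which they will be.

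The cost is SAP wording and three population flags instead of one, with no new data. The downside is that the Day 22 and Day 43 sets will differ slightly, so any within-child comparison of one dose with two should use the children who are in both.

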7.5 Safety Set

Solicited Safety Set

All subjects in the Exposed Set with any solicited AE data collected, including temperature measurements or use of analgesics/antipyretics.

Unsolicited Safety Set

All subjects in the Exposed Set with results of the unsolicited AE assessments recorded. A record of safety assessment performed at a specific time point, with confirmation of no AE, is considered as AE data hence subject is to be included.

Safety Set

All subjects who are in the Solicited Safety Set or in the Unsolicited Safety Set.

Subjects will be analyzed as “treated” (i.e., according to the vaccine a subject actual received as first dose, rather than the vaccine to which the subject may have been randomized).

All immunogenicity analyses (primary, secondary, and exploratory) will be performed on the PPS Immunogenicity. The primary immunogenicity analyses will be also performed based on the FAS Immunogenicity if the percentage of subjects excluded from the PPS immunogenicity is greater than 5%. All solicited safety analyses will be performed in solicited safety set. All unsolicited safety analyses will be performed on the unsolicited safety set.

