6.3 Vaccine Preparation and Administration

The investigator or designee will be responsible for oversight of the administration of vaccine to subjects enrolled in the study according to the procedures stipulated in this study protocol. The study vaccines will be administered only by unblinded personnel who are qualified to perform that function under applicable local laws and regulations for the specific study site.

The study vaccines will be supplied in kits (per subjects/per visit) containing the required materials to administer the specific formulation at the site. The kits may contain the following components, depending on the dose regimen:

- PFS, adjuvanted (50% MF59) H5N1 A/turkey/Turkey/1/2005 1.9 µg/0.25 mL
- PFS, adjuvanted (100% MF59) H5N1 A/turkey/Turkey/1/2005 1.9 µg/0.5 mL
- PFS, adjuvanted H5N1 (50% MF59) A/turkey/Turkey/1/2005 3.75 µg/0.25 mL
- PFS, adjuvanted (100% MF59) H5N1 A/turkey/Turkey/1/2005 3.75 µg/0.5 mL
- PFS, adjuvanted H5N1 (50% MF59) A/turkey/Turkey/1/2005 7.5 µg/0.25 mL
- PFS, adjuvanted (100%) H5N1 A/turkey/Turkey/1/2005 7.5 µg/0.5 mL

All formulations will be supplied as PFSs, depending on the treatment allocation 0.25 mL or 0.5 mL will be administered.

For detailed vaccine preparation and administration instructions unblinded personnel should refer to the IMP handling instructions.

PRECAUTIONS TO BE OBSERVED IN ADMINISTERING STUDY VACCINE:

Prior to vaccination, subjects must be determined to be eligible for study vaccination and it must be clinically appropriate in the judgment of the investigator to vaccinate. Eligibility for vaccination prior to first study vaccine administration is determined by evaluating the entry criteria outlined in protocol [sections 4.1, Inclusion Criteria](#) and [4.2, Exclusion Criteria](#).

Eligibility for subsequent study vaccination is determined by following the criteria outlined in [section 4.3, Criteria for Delay of Vaccination](#).

Eligibility for non-study vaccines should be determined by the investigator, pending the review of the package insert of the relevant vaccine and the guidelines described in [section 6.2, Non-Study Vaccines](#).

Study vaccines should not be administered to individuals with known hypersensitivity to any component of the vaccines.

Vaccine administration will be performed intramuscularly, anterolateral thigh for children ages <2 years; deltoid for children ages \geq 2 years, unless insufficient deltoid mass.

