8.1 Endpoints

8.1.1 Primary Endpoint(s)

8.1.1.1 Primary Safety Endpoint(s)

The measures for assessing safety and reactogenicity are as follows:

- Percentages of subjects with solicited local and systemic AEs¹⁰ that occur within 7 days following each vaccination and calculated for 4 time intervals after vaccination: 30 minutes, 1 through 3 days, 4 through 7 days, and 1 through 7 days.
- Percentages of subjects with any unsolicited AEs reported within 21 days after each vaccination within each vaccine group.
- Percentages of subjects reporting SAEs, NOCDs, AESIs, and AEs leading to vaccine and/or study withdrawal, as collected from Day 1 through Day 387.

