8.3.3 Safety Set

Solicited Safety Set (solicited local and systemic adverse events and other solicited adverse events)

All subjects in the exposed set with any solicited adverse event data and/or indicators of solicited adverse events.

Subjects with a confirmation of no indicators of solicited adverse event (for example vomiting is none or injection site-induration is 0 mm [none]) will be included in this population as well.

Unsolicited Safety Set (unsolicited adverse events)

All subjects in the exposed set with unsolicited adverse event data.

Subjects with a confirmation of no unsolicited adverse event will be included in this population as well.

Overall Safety Set

All subjects who are in the solicited safety set and/or unsolicited safety set.

Subjects will be analyzed “as treated” (ie, according to the vaccine formulation a subject received, rather than the vaccine formulation to which the subject may have been randomized).

Subjects randomized in the wrong age stratum will be reassigned to the correct age stratum and will be analyzed using corrected stratum for all safety sets (ie, solicited safety set, unsolicited safety set and overall safety set). If a subject is unblinded during the study, he/she will be included in all the safety sets.

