4.1.1 Definition of Randomization/Vaccination Errors

The list below provides categories for errors that may occur during vaccination.

Randomization errors:

- Administered wrong kit (Subject was vaccinated with a vaccine different from the one assigned at randomization).

Statistical Analysis Plan, Protocol Number V87_30

06 MAY 2022 Final Version 1.0

Vaccination errors:

- Administered only part of the study vaccine.
- Incorrect vaccine administration
- Administered expired vaccine.
- Administered temperature deviated vaccine.

Stratification error:

- Subject randomized in the wrong stratification stratum.

Randomization and Vaccination errors are considered as major (Clinical Study Report (CSR)-reportable) protocol deviations. Stratification error will not be considered as CSR-reportable protocol deviations (PDs) as there will no impact on the actual formulation administered. Subjects will be included in analysis according to actual age subgroup.

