| | | Arthralgia | No interference with daily activity | Interferes with daily activity | Prevents daily activity |
| | | Headache | No interference with daily activity | Interferes with daily activity | Prevents daily activity |
| | | Malaise | No interference with daily activity | Interferes with daily activity | Prevents daily activity |
| Overall | | Shivering/Chills | No interference with daily activity | Interferes with daily activity | Prevents daily activity |
| Overall | | Fever | 38.0 - 38.9 °C | 39 – 39.9 °C | ≥40.0 °C |

Note: presence of an event on a day is defined as mild, moderate or severe; absence is defined as none. Ecchymosis, Erythema and Induration: grading will be derived from the actual measurements in mm; Fever will be derived from the actual measured body temperature.

Statistical Analysis Plan, Protocol Number V87_30

06 MAY 2022 Final Version 1.0

Other Indicators of Reactogenicity

The use of analgesics/antipyretics will be captured as “absent” or “present” separately by reason “for treatment” or “for prevention”.

The analyses will encompass various summaries of the data by vaccination and – where applicable - combined across the two vaccinations using the solicited safety set:

1. Overall summary of subjects with solicited AEs
2. Solicited local AEs, maximum event severity by event and interval
3. Solicited systemic AEs, maximum event severity by event and interval
4. Number of days of solicited AEs, including ongoing AE after Day 7
5. Daily reports of subjects with solicited AEs, only per vaccination
6. Day of first onset of solicited AEs, only per vaccination
7. Solicited AEs ongoing at Day 7
8. Distribution of maximum temperature
9. Other use of analgesics/antipyretics

For each of the time points or time intervals presented in the summaries, only subjects with at least one valid observation (i.e., any non-missing values but excluding “Not done/unknown” and implausible values) for the solicited adverse events in the interval of interest will be considered. Subjects without valid data will be removed from the denominator to prevent a downward bias (towards zero).

All tables are run by age stratum and vaccine group. The local solicited AEs and the common systemic solicited AEs (as defined in Table 3) are also presented combining the two age strata.

Overall summary of subjects with solicited adverse events.

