Any solicited AE presence is defined as at least one day recorded a presence of a local or a systemic AE. No solicited AE is defined as for all days ‘No’ for all pre-defined solicited AEs. Same convention is used considering local and systemic events separate.

The use of analgesics/antipyretics will be considered as a separate category under “other”.

Solicited local adverse events, maximum event severity by event and interval

The **maximum event severity** will be defined if there is at least one plausible non- missing observation (excluding “Not done/unknown” and implausible values) within this time interval.

Statistical Analysis Plan, Protocol Number V87_30

06 MAY 2022 Final Version 1.0

Each subject's data will be aggregated across the time points of the interval and summarized according to the maximal severity observed for each local AE, followed by a summary across subjects for each vaccine. Subjects without any solicited AEs in the interval, i.e., missing values at each of the requested time points, will be removed from the denominator.

The time intervals will be 30 minutes, Day 1 to Day 7, Day 1 to Day 3 and Day 4 to Day 7. A summary tables will be created with the frequency using only any and severe events.

Solicited systemic adverse events, maximum event severity by event and interval

The analysis on the maximum severity of the systemic adverse events will be done along the same methods as for the local adverse events.

Number of days with solicited adverse events

The number of days with the AE is defined irrespective of severity. If a solicited AE continues beyond day 7 the period after day 7 is added.

The frequency distribution of the number of days will be provided in a summary table by vaccine and by AE.

Daily reports of solicited adverse event

For each of the time points only subjects with at least one plausible observation (i.e., any non-missing values but excluding "Not done/unknown" and implausible values) for the solicited AE in the interval of interest will be considered. Subjects without plausible data (i.e. missing values or reported as "Not done/unknown" and implausible values) will be removed from the denominator to prevent a downward bias (towards zero). Data collected will be summarized (frequencies and percentages of subjects) by vaccine group, solicited AE, vaccination number and time point.

Time of first onset of solicited adverse events

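### SAP 7.5 groups every child in the safety analysis by the first-dose formulation, so a child given two different formulations has dose-2 reactions reported under one not given that day (minor, conditional on kit errors)

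*SAP*

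**What the plan says.** Protocol 8.3.3 assigns children in the safety sets "according to the vaccine formulation a subject received, rather than the vaccine formulation to which the subject may have been randomized". It does not say what to do with a child who received two formulations.

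SAP 7.5 makes the rule specific: "according to the vaccine a subject actual received as first dose, rather than the vaccine to which the subject may have been randomized". SAP 16 lists no changes to the planned analysis.

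The primary solicited safety endpoint is defined for each dose. Protocol 8.1.1.1 counts local and systemic events "that occur within 7 days following each vaccination and calculated for 4 time intervals after vaccination". SAP 13.2 follows this: "The analyses will encompass various summaries of the data by vaccination", with a combination over both doses where applicable. Its daily reports are broken down "by vaccine group, solicited AE, vaccination number and time point". No section of the SAP defines a treatment variable specific to a dose.

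Protocol 6.3 states: "The study vaccines will be supplied in kits (per subjects/per visit". SAP 4.1.1 names a wrong kit among the possible errors ("Subject was vaccinated with a vaccine different from the one assigned at randomization") and does not limit it to the first dose.

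**The concern.** Because kits are separate for each visit, a wrong kit can be given at one visit and the right kit at the other. The first-dose rule then carries the day-1 formulation into the dose-2 tables. Those tables are meant to describe reactions in the 7 days after the second injection, so the natural column is the formulation injected that day.

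The SAP deals with wrong kits for immunogenicity: the FAS is analysed as randomised (7.3), and the PPS requires that the randomised vaccine was received (7.4). The PPS rule does not reach the safety sets, so an affected child stays in the safety tables.

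Reactogenicity by formulation is a primary safety result of a dose-ranging trial. A misplaced child carries a reaction from one antigen or adjuvant content to another. A common mild reaction would barely register, but one severe reaction could be the only such event in a small column.

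**Working it through.** **Step 1. Where the rule puts each child.** Take a child randomised to A and let F stand for any other formulation.

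| Dose 1 given | Dose 2 given | Column under SAP 7.5 | Dose-2 table matches the formulation given that day? |
|---|---|---|---|
| A | A | A | Yes |
| A | F | A | No: reactions after F are shown under A |
| F | A | F | No: reactions after A are shown under F |
| F | F | F | Yes |

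The problem is confined to the two middle rows. Dose-1 tables are correct in all four.

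**Step 2. Denominators.** SAP 5 gives 420 randomised. Protocol Table 6.1 gives about 70 per arm and 35 per arm and age cohort. These reproduce: 420/6 = 70 and 420/12 = 35. SAP 13.2 runs all solicited tables by age stratum (n = 35) and adds combined tables for local and common systemic events (n = 70).

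**Step 3. Ceiling per misplaced child.** Let a column of n children contain one misplaced child who reacted and x other children who reacted. The reported rate is (x + 1)/n, and without the child it is x/(n − 1). The difference is (n − 1 − x)/[n(n − 1)]. It is largest at x = 0, where it equals 1/n:

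- n = 70: 1/70 = 1.43 points
- n = 35: 1/35 = 2.86 points

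The ceiling is reached only when no correctly placed child reacted, which is the situation of a rare severe reaction.

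**Step 4. Expected shift.** Let p be the true dose-2 rate for the column's formulation, q the rate for the formulation given, and k the number of misplaced children in the column. The reported rate has expectation [(n − k)p + kq]/n, so the shift is k(q − p)/n. The documents give neither reaction rates nor a wrong-kit rate, so p, q and k are assumptions.

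| p, q (assumed) | n | k = 1 | k = 5 |
|---|---|---|---|
| 30%, 50% | 70 | 0.29 points | 1.43 points |
| 30%, 50% | 35 | 0.57 points | 2.86 points |
| 20%, 60% | 70 | 0.57 points | 2.86 points |
| 20%, 60% | 35 | 1.14 points | 5.71 points |

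**Step 5. A plausible total.** If 0.5% to 1% of 420 second doses were affected (assumption), that is about 2 to 4 children, or 0.33 to 0.67 per arm on average. With q − p between 20 and 40 points, the average shift at n = 70 runs from 0.33 × 20/70 = 0.1 to 0.67 × 40/70 = 0.4 points. With no wrong kits it is zero.

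**The case against.** The strongest defence is that the trial compares two-dose regimens and the safety objective is stated per vaccine group. A child given A then F is not a clean dose-2 observation of F either, because the first exposure was A. One group per child is a recognised convention and keeps column totals constant across tables. It stands for outcomes that span both doses, such as SAEs, AESIs and NOCDs to Day 387. It does not rescue the per-dose tables: the same mixed exposure sits in the column that the SAP uses now, and there the formulation given that day is wrong as well.

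Other mitigating points also stand. Randomisation and pack assignment are automated (Protocol 5.1.4). Wrong kits are major, reportable deviations (SAP 4.1.1). Deviations and adverse events are listed by subject (SAP 6.1 and 13.3), so affected children can be found. The analysis is descriptive, with no success criterion that could turn on a misplaced child.

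A reader might infer more than the documents support:

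- **That the SAP contradicts the protocol, or that SAP 16 hides a change.** Protocol 8.3.3 is silent on two formulations, so the SAP supplies a tie-break. At most it could have been noted.
- **That the result is neither as treated nor as randomised.** For a dose-2 error after a correct dose 1, the child is analysed exactly as randomised.
- **That two arms are distorted.** The column for the formulation actually given loses one observation, but the omission does not bias it.
- **That kit errors are forecast.** SAP 4.1.1 lists kinds of error that could happen and gives no frequency.

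**Conclusion.** The point holds as a minor, conditional gap. For a child who receives different formulations at the two doses, the dose-2 solicited tables report reactions under a formulation not given that day. Nothing elsewhere in the SAP overrides this.

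The 1.4 and 2.9 point figures are ceilings per affected child, not estimates of bias. At the assumed wrong-kit rates, the average shift in common reactions is a fraction of a point. The gap matters mainly for infrequent severe reactions in the 35-child cells, where one event can be the whole count. The sizes rest on the planned arm sizes and on assumed reaction and error rates. The placement of the child rests only on the text of SAP 7.5 and 13.2.

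**What to change.** In SAP 7.5 and 13.2:

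- Define an actual-treatment variable for each vaccination, and group every by-vaccination solicited table by the formulation received at that vaccination.
- Keep the first-dose rule for tables combined over both doses and for whole-study summaries (SAEs, AESIs, NOCDs).
- List all children who received two formulations, with the formulation given at each dose.

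In SAP 16, record the safety grouping rule as a refinement of Protocol 8.3.3.

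The cost is a few sentences, one derived variable and one listing. Trial conduct and data collection do not change, since Protocol 6.6 already requires each administration to be documented. The downside is that dose-2 column totals may differ by a few children from the combined tables, which a footnote can explain.
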